### ***9.3. Subject Status and Classification***

Subjects who provide written informed consent but do not meet all of the study eligibility criteria will not be implanted or activated. These subjects will be deemed as "enrolled but not activated" and their reason for ineligibility will be documented.

Enrolled subjects who are not activated will not count towards the enrollment cap. Subjects who sign consent, meet all eligibility criteria, undergo permanent implant and are activated cannot be replaced.

#### 9.4. *Enrollment Controls*

The study will implement a formal *Enrollment Communication Plan*. The plan will outline the specific activities, as well as the nature and timing of communications to investigators in order to minimize the risk of enrollment beyond the protocol-specified enrollment caps determined by the statistical analysis plan.

#### 9.5. *End-of-Study Action Plan*

When each subject completes the 2-Year Visit or withdraws, the subject exits the study and ends study participation. Subjects may continue to use their system per the applicable Directions for Use and will be followed according to standard of care. Boston Scientific Neuromodulation Corporation will not pay for visits that occur after a subject completes the 2-Year Visit, withdraws or is determined to be lost to follow-up.

If the study is terminated early due to sponsor discretion or due to the discovery of an unexpected, significant, or unacceptable risk/safety concern regardless of how far along the subject has reached in their study follow-up, subjects will be followed according to standard of care. Sites will have 30 days to notify all subjects of study closure.

If device implantation is unsuccessful, the subject will be followed for 2 weeks post implantation attempt to assess for procedure related adverse events. If the device is explanted, the subject will be followed for 2 weeks post explant to assess for related adverse events.

Device related adverse events and/or deficiencies occurring after study participation, withdrawal from the study, or after the specified timeframe following unsuccessful trials, implant failures, and explants, should be reported to BSN Patient Care at: [contact]. Such complications should not be captured as adverse events in the study.

## 10. Study Methods

### 10.1. *Data Collection*

The data collection schedule is shown in table below.

[REDACTED]

[REDACTED]

[REDACTED]

[REDACTED]

[REDACTED]

[REDACTED]

[REDACTED]

[REDACTED]

[REDACTED]

[REDACTED]

### 10.2. Study Candidate Screening

Subjects' eligibility for the study will be assessed based on study Inclusion and Exclusion criteria listed in Sections 8.2 and 8.3, respectively. Subjects who have provided informed consent and who have been determined to not meet all eligibility requirements will be withdrawn.

### 10.3. Informed Consent

Written Informed Consent must be obtained for all patients who are potential study candidates. Study candidates will be asked to sign the Informed Consent form before any study-specific tests or procedures are performed.

- The context of the study must be fully explained to the patient and patients must be given an opportunity to ask questions and have those questions answered to their satisfaction.
- Study personnel should explain to each potential participant that even if he or she agrees to participate in the study and signs an informed consent form, further testing might demonstrate that he or she is not eligible for the study.
- Written informed consent must be recorded appropriately by means of the subject's dated signature.
- The consent process must be documented in the subject's medical chart.

Research study candidates in the State of California will also be provided with the California Experimental Patient's Bill of Rights

#### 10.3.1. Screening Period

Subjects undergo screening related procedures to determine eligibility for the study. It will take until permanent implantation is complete to determine all eligibility requirements.

[REDACTED]

[REDACTED]

[REDACTED]

**10.4. Opioid Medication Lock Visit (Up to 35 days following informed consent)**

The Opioid Medication Lock Visit will occur within 35 days following informed consent. However, this visit may occur on the same day as that of the Informed consent as well following completion of consent.

At this visit, the subject's opioid pain medications will be locked, with no increase in type/dose/route/frequency, until the 3-Month post-activation Visit.

At this visit (or during the screening period), the investigator will convert the subject's opioid medication prescriptions from PRN to a fixed dose, as needed.

Subjects will be reminded to continue to use their in-home devices the mobile app., as applicable.

Subjects who are not taking opioid medications are not required to Opioid Medication Lock Visit, and can proceed to their Baseline Visit. Subjects who are not taking opioid medications will maintain this status until the 3-Month post-activation Visit.

**10.5. Baseline Period (14 days)**

The Baseline Period will last for 14 consecutive days following the Opioid Medication Lock Visit. At the end of the Baseline Period, subjects will return to the clinic for their Baseline Visit.

Subjects are to not make any increases to their opioid pain medications during this period.

**10.6. Baseline Visit (0 – 7 days post Baseline Period)**

At the Baseline Visit, subjects will return to the clinic to complete remaining screening requirements. Subjects should bring in their phone with mobile app to this visit. Any adverse since the last study visit will be collected.

[Redacted]

- [Redacted]
- [Redacted]
- [Redacted]
- [Redacted]
- [Redacted]
- [Redacted]
- [Redacted]
- [Redacted]
- [Redacted]
- [Redacted]
- [Redacted]

[REDACTED]

- [REDACTED]
- [REDACTED]
- [REDACTED]
- [REDACTED]

Subjects that meet all study criteria will be scheduled for the device implant procedures (trial and permanent implant of the SCS system). If a subject fails to meet eligibility criteria, they will be withdrawn from the study.

[REDACTED]

- [REDACTED]
- [REDACTED]

**10.7. Implant Procedures (Up to 90 days following the Baseline Visit)**

Subjects will have up to 90 days following the Baseline Visit to receive their WaveWriter System.

[REDACTED]

[REDACTED]

Subjects with an unsuccessful implant procedure will be followed for 2 weeks for procedure related adverse events then withdrawn from the study. Acute opioid pain medications may be taken.

**10.8. Healing Period (14 - 28 days following Implant Procedures)**

The subject's device will remain inactivated (device OFF) for 14 to 28 days following the permanent implantation procedure to allow for healing. Acute opioid pain medications may be taken during this period. No additional scheduled assessments will be completed during this period.

**10.9. Activation Visit (Day 0)**

At the Activation Visit, subjects' device will be activated. Subjects should bring their phone with mobile app to this visit.

[REDACTED]

- [REDACTED]
- [REDACTED]
- [REDACTED]
- [REDACTED]

**10.10. Programming Lock Visit (Day 70 - 7 days post-activation Visit)**

At the Programming Lock Visit, subjects will return to the clinic to have their programs locked. Any protocol required adverse events since the last study visit will be collected.

No further changes to the subject's programs (for e.g. electrode configuration) will be

[REDACTED]

- [REDACTED]
- [REDACTED]
- [REDACTED]
- [REDACTED]

- [REDACTED]

**10.12. 6-Month Visit (180 ± 30 days post-activation Visit)**

During the 6-Month Visit, subjects will return to the clinic for study evaluations and programming. Any protocol required adverse events since their last study visit will be collected.

[REDACTED]

[REDACTED]

- 1. [REDACTED]
- 2. [REDACTED]
- 3. [REDACTED]
- 4. [REDACTED]
- 5. [REDACTED]
- 6. [REDACTED]
- 7. [REDACTED]
- 8. [REDACTED]
- 9. [REDACTED]
- 10. [REDACTED]
- 11. [REDACTED]
- 12. [REDACTED]
- 13. [REDACTED]
- 14. [REDACTED]
- 15. [REDACTED]
- 16. [REDACTED]
- 17. [REDACTED]
- 18. [REDACTED]
- 19. [REDACTED]
- 20. [REDACTED]
- 21. [REDACTED]
- 22. [REDACTED]
- 23. [REDACTED]
- 24. [REDACTED]
- 25. [REDACTED]
- 26. [REDACTED]
- 27. [REDACTED]
- 28. [REDACTED]
- 29. [REDACTED]
- 30. [REDACTED]
- 31. [REDACTED]
- 32. [REDACTED]
- 33. [REDACTED]
- 34. [REDACTED]
- 35. [REDACTED]
- 36. [REDACTED]
- 37. [REDACTED]
- 38. [REDACTED]
- 39. [REDACTED]
- 40. [REDACTED]
- 41. [REDACTED]
- 42. [REDACTED]
- 43. [REDACTED]
- 44. [REDACTED]
- 45. [REDACTED]
- 46. [REDACTED]
- 47. [REDACTED]
- 48. [REDACTED]
- 49. [REDACTED]
- 50. [REDACTED]
- 51. [REDACTED]
- 52. [REDACTED]
- 53. [REDACTED]
- 54. [REDACTED]
- 55. [REDACTED]
- 56. [REDACTED]
- 57. [REDACTED]
- 58. [REDACTED]
- 59. [REDACTED]
- 60. [REDACTED]
- 61. [REDACTED]
- 62. [REDACTED]
- 63. [REDACTED]
- 64. [REDACTED]
- 65. [REDACTED]
- 66. [REDACTED]
- 67. [REDACTED]
- 68. [REDACTED]
- 69. [REDACTED]
- 70. [REDACTED]
- 71. [REDACTED]
- 72. [REDACTED]
- 73. [REDACTED]
- 74. [REDACTED]
- 75. [REDACTED]
- 76. [REDACTED]
- 77. [REDACTED]
- 78. [REDACTED]
- 79. [REDACTED]
- 80. [REDACTED]
- 81. [REDACTED]
- 82. [REDACTED]
- 83. [REDACTED]
- 84. [REDACTED]
- 85. [REDACTED]
- 86. [REDACTED]
- 87. [REDACTED]
- 88. [REDACTED]
- 89. [REDACTED]
- 90. [REDACTED]
- 91. [REDACTED]
- 92. [REDACTED]
- 93. [REDACTED]
- 94. [REDACTED]
- 95. [REDACTED]
- 96. [REDACTED]
- 97. [REDACTED]
- 98. [REDACTED]
- 99. [REDACTED]
- 100. [REDACTED]

The 2 Year Visit is the End of Study Visit and End of Study Action Plan (ESAP) will be followed as described in Section 9.5.

**10.15. *Unscheduled Visit***

Subjects may have as many unscheduled visits as required for device-related in-office or procedure visits (e.g., optimization of programming during the programming period) or for evaluation of possible adverse events and if applicable, re-positioning, replacement or explant of a device component. Unscheduled visit information will be captured, as applicable.

**10.15.1. Revision or Replacement of Leads, Extensions and/or IPGs**

During the study, it is possible that leads may be placed incorrectly, migrate, or malfunction and require repositioning or replacement. It is also possible that the extensions or splitters or IPG may be uncomfortable or malfunction and may require repositioning or replacement. The decision to reposition or replace any device component will be made by the investigator and only if the subject agrees. Subjects not agreeing to a recommended lead revision will be withdrawn from the study but will be included in the intent-to-treat and safety analyses. Subjects agreeing to revision will continue study and will be followed according to the original study schedule. Effectiveness data from these subjects will be included in the intent to treat analysis. Lead revisions/replacements for correcting for migration and/or malfunction must be performed as soon as is reasonably possible following determination of the need for revision/replacement.

The investigator should notify Boston Scientific prior to any study procedures. Any replacements or revisions performed during the study should be recorded in the EDC system, including information about the procedure, device, and/or adverse event if applicable. Information on assessing revisions or replacements of leads, extensions or IPGs as adverse events is described in Safety Reporting Section.

[REDACTED]

[REDACTED]

[REDACTED]

**10.17. Study Completion**

All activated subjects permanently implanted will be followed through completion of the 2-Year Visit or study withdrawal. The End of Study Action Plan defines the actions to be taken when the subject reaches the end of their study participation.

**10.18. Source Documents**

It is preferable that original source documents are maintained, when available. In lieu of original source documents, certified copies are required to be maintained. A certified copy is a copy (irrespective of the type of media used) of the original record that has been verified (i.e., by a dated signature or by generation through a validated process) to have the same information, including data that describe the context, content, and structure, as the original. Source documentation includes but is not limited to those items noted in Table 10.18-1.

**Table 10.18-1: Source Documentation Requirements**

Requirement	Disposition
Hospital records and/or clinical and office charts including the evidence of but not limited to inclusion/exclusion criteria, informed consent, procedures, exams, SCS System procedure(s) and devices used, evaluations,	Retained at investigational site

**Table 10.18-1: Source Documentation Requirements**

Requirement	Disposition
health economic assessments, laboratory results, medications, assessment of adverse events.	
Assessments and questionnaires	Retained at investigational site and/or electronic data collection platform/EDC
Programming information	Retained at investigational site and/or electronic data collection platform/EDC
Imaging films/prints documenting lead(s) location	Retained at investigational site

## 11. Statistical Considerations

### 11.1. Endpoints

#### 11.1.1. Primary Endpoint

The primary endpoint for this study is the proportion of subjects with 50% or greater reduction from Baseline Visit in average targeted pain intensity at 3 months post-activation with no increase in baseline average opioid medications used to treat pain.

##### 11.1.1.1. Hypotheses

The primary statistical hypothesis in this study is that the proportion of subjects with 50% or greater reduction from Baseline Visit in average daily targeted pain intensity at 3 months post-activation is non inferior, compared to an Objective Performance Criteria (OPC) of 40%.

$$H_0: \pi_{\text{opc}} - \pi_t \geq 0.20$$

$$H_1: \pi_{\text{opc}} - \pi_t < 0.20$$

Where  $\pi_t$  is the proportion of subjects with 50% or greater reduction from Baseline in average daily targeted pain intensity at 3 months post-activation with no increase in baseline average daily opioid pain medications,  $\pi_{\text{opc}}$  is the responder rate of an OPC based on Kumar paper (Kumar 2008). The study's non-inferiority margin is 0.20.

[REDACTED]

## 11.2. General Statistical Methods

### 11.2.1. Analysis Sets

- **Intent-to-Treat (ITT) Population:** All subjects who receive the study device and are activated, regardless of the treatment received.
- **Per Protocol (PP) Population:** All subjects who receive the study device, with no major protocol deviations.
- **Safety Population:** All subjects who sign the IRB-approved written Informed Consent form

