### 6.6. *Safety Parameters*

Safety parameters include the rates of occurrence of all device hardware, device stimulation and procedure related non-serious adverse events, all serious adverse events, and unanticipated adverse events through the end of the study.

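### Device- and procedure-related event rates would be understated if divided by the all-consented Safety Population; confirm or state exposed-subject denominators, and reconcile sections 9.1 and 11.2.1

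*Combined protocol and SAP*

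**What the plan says.** Section 6.6 lists as safety parameters "the rates of occurrence of all device hardware, device stimulation and procedure related non-serious adverse events, all serious adverse events", together with unanticipated events, through the end of the study. It gives no denominator.

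Section 11.2.1 defines three analysis sets. The Safety Population is "All subjects who sign the IRB-approved written Informed Consent form", with no exposure condition. The ITT Population is "All subjects who receive the study device and are activated, regardless of the treatment received". The Per Protocol Population is the device recipients without major deviations.

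Section 9.1 places enrollment at consent signature. It then says that enrolled and activated subjects are the ones included in the study analyses.

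Several sections show who falls between consent and activation:

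- Section 9.3: "Subjects who provide written informed consent but do not meet all of the study eligibility criteria will not be implanted or activated". Non-activated subjects do not count toward the enrollment cap.
- Section 10.6, at the Baseline Visit: "If a subject fails to meet eligibility criteria, they will be withdrawn from the study". Those who qualify go on to the procedures: "Subjects that meet all study criteria will be scheduled for the device implant procedures (trial and permanent implant of the SCS system)".
- Section 10.3.1: "It will take until permanent implantation is complete to determine all eligibility requirements".
- Section 9.5 mentions reporting "after the specified timeframe following unsuccessful trials, implant failures, and explants". Section 10.7 has subjects with an unsuccessful implant followed for 2 weeks for procedure-related events and then withdrawn.
- Section 11.2.2 has the reasons recorded in EDC for consented subjects who are not implanted.

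Section 17.1 has reportable events recorded from consent onward.

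**The concern.** A subject who leaves before any trial or implant procedure cannot have an event caused by the procedure, the hardware or the stimulation. Counting that subject in the denominator lowers the rate for a reason unrelated to the device, and the rate falls further as more people leave early. No visible rule limits how many such subjects there may be, because non-activated subjects sit outside the cap.

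Section 9.1 points the other way. An activated-only set removes the unexposed, but it also removes subjects whose trial failed or whose implant was unsuccessful. Those subjects are exposed, and the protocol follows unsuccessful implants specifically for procedure-related events. The visible text therefore offers two candidate denominators, and neither matches the population at risk.

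At stake is how the study's safety rates read, and whether they can be compared with studies that lose a different share of subjects before the procedure.

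**Working it through.** The visible documents state no sample size, event rate or screen-failure share, so there is no figure of the plan's own to reproduce. The check is an identity plus illustrations whose inputs are all assumed.

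**Identity.** Let E be the exposed subjects (any trial or implant procedure attempted), C the consented subjects, x the exposed subjects with at least one related event, and f = E / C. Unexposed subjects contribute no such events, so:

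- rate on consented = x / C = (x / E) × (E / C) = rate on exposed × f
- relative understatement = 1 − f, the unexposed share

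This is a relative reduction, not a number of percentage points.

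**Range (f assumed, true rate assumed 10%).**

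| f | Unexposed share | Rate shown on consented |
|---|---|---|
| 0.9 | 10% | 10% × 0.9 = 9.0% |
| 0.7 | 30% | 10% × 0.7 = 7.0% |
| 0.5 | 50% | 10% × 0.5 = 5.0% |

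**Why non-activated is not the same as unexposed.** Assume 143 consented, 120 with a trial or implant procedure attempted, and 100 activated. Assume 12 subjects with a procedure-related event, 9 of them activated and 3 never activated.

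- Exposed: 12 / 120 = 10.0%.
- All consented: 12 / 143 = 8.4%. Here f = 120 / 143 = 0.839, so the understatement is 1 − 0.839 = 16.1%.
- Non-activated share: 1 − 100 / 143 = 30.1%. Using this as the dilution would overstate it, because 120 − 100 = 20 non-activated subjects were exposed.
- Activated only: 9 / 100 = 9.0%, losing 3 of 12 affected subjects (25%).

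The error from an activated-only set has no fixed direction. In this example the 20 exposed but never activated subjects have a rate of 3 / 20 = 15%, above the 9% in activated subjects, so leaving them out lowers the rate. If they had fewer events than activated subjects, leaving them out would raise it. By contrast, the consented denominator can only lower the rate.

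These cohorts show the mechanism and do not estimate anything for this trial.

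**The case against.** The strongest objection is that no visible passage ties the 6.6 rates to the Safety Population. Section 11.2.1 says who belongs to the set, not that every safety percentage is divided by it, and event-specific table denominators could sit alongside it. The places where such a rule would be found are redacted: text after 11.2.2 is blacked out, and 11.2.4 breaks off while referring to further detail. Redacted text cannot be counted as missing. This stands, and it is why the point is conditional.

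The term for rates in 6.6 is also undefined. The identity above is for subject proportions; a rate per unit of time would need its own at-risk time. This stands too.

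The consented set is also suitable for part of the task. Events are recorded from consent and all serious events are a safety parameter, so a reader who infers that the Safety Population definition is itself wrong goes too far. The set even keeps the failed trials and unsuccessful implants that ITT would drop.

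Two other stronger readings are tempting. One is that the plan does divide these rates by all consented subjects; the visible text does not say so, and 9.1 points elsewhere. The other is that the dilution equals the whole non-activated share. Sections 9.5, 10.6 and 10.7 rule that out, because a trial comes before permanent implant and some non-activated subjects have had a procedure.

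Finally, the size rests entirely on assumption: f could be close to 1. What survives is that the one visible safety set, applied as written to these rates, gives diluted figures, and that 9.1 and 11.2.1 do not point to the same subjects.

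**Conclusion.** The point holds in conditional form. If the device- and procedure-related rates are subject proportions over the Safety Population, they are understated in relative terms by exactly the share of consented subjects who never had a trial or implant procedure. That share is not in the documents; at 10% to 50%, which is assumed, a 10% rate would show as 9% to 5%. The result also assumes that the procedure in question is the trial or implant, so that subjects without either cannot have a related event.

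Section 9.1, read as an activated-only set, avoids this dilution but drops exposed subjects. The two sections need to be reconciled whatever the redacted text says.

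The severity is minor: the study is single-arm, no visible safety hypothesis rests on these rates, and the primary endpoint and event counts do not change. Confidence is low, because the denominator rule may already exist in text that cannot be seen.

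**What to change.** - Keep the all-consented set for event listings and for serious events counted from consent (17.1).
- Report device- and procedure-related rates over subjects with any trial or implant procedure attempted, including unsuccessful ones. Show the number of subjects at each stage: attempted, implanted, activated. Stimulation-related rates may use subjects who received any stimulation, including during the trial.
- Do not use ITT for these rates, since it requires activation.
- Reconcile the 9.1 statement on who is analysed with the Safety Population in 11.2.1.

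If the redacted statistical text already sets exposed-subject denominators, only the last step is needed.

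The cost is SAP wording and table denominators. Reported device and procedure rates will be somewhat higher if the alternative was the consented set. Exposure status must come from procedure and device records. Table 10.18-1 lists SCS procedures, devices used and programming information among the source documents, but the collection schedule in 10.1 is redacted, so it cannot be confirmed here that trial-stage exposure is already captured in EDC.

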### 11.2.2. Control of Systematic Error/Bias

Selection of patients will be made from the Investigator's usual patient load. All patients meeting the inclusion/exclusion criteria and having signed the Informed Consent Form will be eligible for participation in the study. The reasons for exclusion, for subjects who sign an informed consent form but are not implanted, will be indicated in EDC. Boston Scientific will report to the ethic committee any evidence of fraud, including deliberate tampering with the selection of subjects.

[REDACTED]

